3.1.1 Sequence of treatment arms and cohorts

A dose level of BI 1387446 will always be explored as single agent first. Only once determined to be safe as single agent, this dose of BI 1387446 will be used in combination with ezabenlimab (BI 754091), always lagging at least one dose level behind when administered in combination with BI 754091.

[figure not shown]

Figure 3.1.1: 1 Sequence of cohorts. BI446: BI 1387446, PD1: ezabenlimab (BI 754091).

Patients with progressive disease on BI 1387446 monotherapy (Arm A) may cross over to the combination (Arm B) after completion of cycle 1 and will be treated at the highest dose level declared to be safe by the SMC at this time. These patients will continue treatment in combination by re-starting treatment at Cycle 1 Day 1 in Arm B. These patients will be analysed in Arm A as long as treated with monotherapy. Instead of completing the REP after monotherapy, patients may cross over to Arm B without repetition of all screening procedures, but will have to undergo a limited set of assessments as specified in [Section 6.2.1](#). A minimum interval of 7 days must have elapsed between last dose of BI 1387446 in Arm A and first dose of ezabenlimab (BI 754091) or BI 1387446 in Arm B. Cross-over patients will be included together with other 'backfill patients' (patients enrolled to backfill cohorts at dose levels that do not exceed the MTD, see [Section 3.1.2](#) for details) in the safety and efficacy assessment in Arm B, but will not be considered for the main analysis of the MTD. For the main analysis of the MTD, cross-over patients will only be included while being treated with BI 1387446 monotherapy in Arm A. However, cross-over patients will be included in the sensitivity analyses of the MTD and thus be considered in addition (refer to [Section 7](#) for details).

Arm B will open at the starting dose level once the starting dose level in Arm A is considered safe by the SMC.

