3.1.2 Method of assigning patients to individual treatment cohorts

Treatment Arms A and B will be started sequentially. Arm A will start first. Once the first dose level in Arm A has been determined to be safe, Arm B may be initiated.

Minimum number of patients for each dose level within a treatment arm

Dose escalation decisions will be based on occurrence of DLTs.

Following the occurrence of a drug related Grade 2 or greater AE, excluding asymptomatic Grade 2 laboratory abnormalities that resolve without medical intervention within 48 hours and transient Grade 2 local injection site reactions that resolve within 48 hours (whereby supportive treatment is allowed), a minimum of 3 patients will be required per dose cohort. The SMC will decide on further trial conduct based on data from the minimum number of patients or can recommend to enroll additional patients at a given dose level.

Maximum number of patients for each dose level within a treatment arm

Once a dose cohort in a treatment arm has been determined to be safe and patient allocation to the next higher dose level is completed, additional patients may be enrolled into the same treatment arm at lower dose levels previously determined to be safe. This so called 'backfill' is intended to enlarge the safety and activity dataset, and to serve as a basis for selection of the RD-P2 in case of a non-linear dose-response relationship. A dose level in a treatment arm will not recruit more than 8 patients which have completed at least one treatment cycle, unless the SMC decides that more patients are needed to perform an adequate safety assessment or to account for patients who have crossed over from Arm A to Arm B. That is, each dose level in a treatment arm will enroll in the lower doses at least 1 patient, unless a Grade 2 or greater AE occurred (with the above exceptions), then at least 3 patients will be enrolled, and an intended maximum of 8 patients, and in the higher doses at least 3 patients and an intended maximum of 8 patients.

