10.5 STATISTICAL APPENDIX

A joint BLRM with overdose control will be used to guide dose escalation in Arms A and B of the trial. The model is introduced in [Section 7](#), which also specifies the priors for the model. After patients in each cohort have completed at least one cycle of treatment, the prior distribution will be updated through No-U-Turn sampling procedures (Hamiltonian Monte Carlo, [[R21-3791](#)]) with the accumulated DLT data from the MTD evaluation period. Posterior probabilities for the rate of DLTs will be summarised from the joint BLRM for Arms A and B. Selection of the next dose in each arm will be based on these probabilities as well as on other safety and laboratory data.

The purpose of this statistical appendix is to present performance metrics (operating characteristics) that illustrate the precision of the design in estimating the MTD under various dose-toxicity relationships through computer simulation. These results are summarised in [Table 10.5: 3](#). For simplicity reasons, a cohort size of 3 patients who are all evaluable starting at 50 µg (Arms A and B) is assumed for calculation of the operating characteristics.

In addition, recommendations of the next dose level in each arm by the joint BLRM with overdose control principle are also provided under various hypothetical outcome scenarios to show how it facilitates on-trial dose-escalation decisions (see [Table 10.5: 1](#)).

Hypothetical data scenarios

Hypothetical data scenarios are shown in [Table 10.5: 1](#) for Arms A and B. These scenarios reflect potential on-trial data constellations and related escalation as allowed by the model and the 100% escalation limit. For each scenario and each arm, the probability of overdose for the current dose, as well as the next potential dose and related probabilities of under-dosing, target dose and over-dosing are shown.

For example, Scenario 1 represents the case where 2 patients have been treated at the starting dose of [REDACTED] Arm A and did not experience a DLT. In Arm B no patients have been treated yet in this scenario. Then, the BLRM would allow for an escalation up to [REDACTED] as the next dose in Arm A. Since escalation is only allowed up to [REDACTED] per protocol, the next dose to be tested in Arm A of the trial would be [REDACTED]

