Similarly, Scenarios 4 and 7 represent cases where no patient in either arm has a DLT. In these cases, the model recommends escalating to higher doses. In some cases the recommended doses exceed the protocol specified margin given by the 100% escalation rule. The next tested dose in these scenarios will always be the dose given by the 100% rule.

Scenario 2 shows that if one of 2 patients treated with the starting dose level in Arm A has a DLT, the EWOC criterion does not allow any of the pre-specified dose levels. Doses lower than [REDACTED] could be chosen in practice if agreed between sponsor and SMC. In particular, starting Arm B at the intended dose level of [REDACTED] would not be allowed based on the overdose control of the BLRM.

Scenario 3 shows the case that already the starting dose level is very toxic, with 2 out of 2 treated patients experiencing a DLT. The overdose control implemented in the model then does not allow going to any of the pre-specified doses.

Scenario 02 represents the case where one patient has been treated at the starting dose of [REDACTED] in Arm A and has experienced a DLT. Based on the BLRM the probability for overdosing at the current dose is 0.656 and the model does not allow treating further patients on 50 µg in Arm A.

In scenario 03, three patients were treated at [REDACTED] in Arm A of which only the first one experienced a DLT, i.e. no DLTs were observed in the additional two patients. In this scenario the model again does not allow any of the pre-specified dose levels, indicating that any DLT in the first cohort leads to recommended doses [REDACTED]

Only if none of the patients in the first cohort [REDACTED] experience DLT (Scenarios 04 and 4), the model allows escalation [REDACTED]. While doses up [REDACTED] Arm A and [REDACTED] in Arm B would be allowed by the EWOC principle in Scenario 4, the recommended next dose in Arm A would be [REDACTED] (due to the maximum increment of 100%) and the starting dose in Arm B would be [REDACTED]

Scenario 05 follows scenario 04 and represents the case in which three patients were treated at the second dose level [REDACTED] in Arm A. One patient experienced a DLT. In this scenario, no escalation [REDACTED] is allowed, but further patients can be treated [REDACTED]

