§ None of the pre-specified doses in the CTP would be allowed based on EWOC, lower doses than the pre-specified ones could be chosen in practice if agreed between sponsor and SMC.

Operating characteristics

Operating characteristics are a way to assess the long-run behaviour of a model by illustrating the precision of the design in estimating the MTD. Under an assumed true dose-toxicity curve, metrics such as the probability of recommending a dose with true DLT rate in the target interval can be approximated via simulation. [Table 10.5: 2](#) describes 7 assumed true dose-toxicity scenarios for Arms A and B which were used to assess the operating

characteristics of the joint model for these arms. The toxicity scenarios reflect a wide range of possible cases as follows:

- Scenario 1: moderate-toxicity scenario
- Scenario 2: high-toxicity scenario
- Scenario 3: low-toxicity scenario
- Scenario 4: non-logistic dose-toxicity scenario
- Scenario 5: all planned doses in overdose range

For Arms A and B, two additional scenarios were used to assess the operating characteristics, especially to assess the effect of the interaction between BI 1387446 and ezabenlimab (BI 754091).

- Scenario 6: data for ezabenlimab (BI 754091) largely deviates from data for BI 1387446, represented by a very flat dose-toxicity curve (as indicated by currently available data on ezabenlimab (BI 754091)) that lies in the overdose range (indicating a quite toxic behaviour of BI 1387446, contrarily to the ezabenlimab (BI 754091) data, which indicate a very low toxicity overall)
- Scenario 7: Large interaction effect between BI 1387446 and ezabenlimab (BI 754091)

Table 10.5: 2

Assumed true dose-toxicity scenarios for Arms A and B

Scenario	Arm		Dose					
			0.075	0.099	0.136	0.203	0.350	0.524
1: Moderate	A		0.075	0.099	0.136	0.203	0.350	0.524
	B		0.157	0.176	0.210	0.276	0.424	0.566
2: High Tox	A	P(DLT)	0.134	0.179	0.287	0.326	0.478	0.579
	B		0.157	0.206	0.291	0.383	0.490	0.592
3: Low Tox	A		0.014	0.076	0.112	0.185	0.201	0.249
	B		0.081	0.104	0.162	0.198	0.235	0.287
4: Non-Logistic	A		0.014	0.076	0.112	0.326	0.478	0.579
	B		0.081	0.104	0.162	0.383	0.490	0.592
5: All too toxic	A		0.341	0.378	0.403	0.457	0.526	0.599
	B		0.367	0.400	0.489	0.534	0.596	0.626
6: Large deviation	A		0.075	0.099	0.136	0.203	0.350	0.524
	B		0.351	0.356	0.359	0.361	0.368	0.370
7: High interaction	A		0.075	0.099	0.136	0.203	0.350	0.524
	B		0.172	0.211	0.292	0.472	0.780	0.927

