Numbers in bold represent assumed toxicity probabilities lying in the target toxicity interval

For each of these scenarios, 1000 trials were simulated. Each cohort consisted of 3 patients and dose escalation complied with the following rules:

- Escalate to the dose which maximises the probability of the targeted toxicity region and satisfies the overdose criterion if it is $\leq 100\%$ increase from the current dose
- If the recommended dose satisfying the overdose criterion is $> 100\%$ increase in dose, then escalate to the dose level with the highest posterior probability that the true DLT rate lies in the target interval which is still $\leq 100\%$ increase from the current dose.

The MTD was considered reached (per arm) if at least 12 patients have been evaluated in the specific trial arm, a dose level is the model's recommendation for the next dose cohort two times in a row, and if for this dose the posterior probability of targeted toxicity was at least 50% or at least 6 patients have been treated at this dose in the respective arm of the trial. In this case, the dose satisfying these conditions is declared MTD of the trial arm, in accordance with the rules stated in [Section 7](#). It was then assessed how often a dose was declared as MTD with true DLT rate in the under-, targeted or over-dose range. Furthermore, the average, minimum and maximum number of patients per simulated trial and the average number of DLTs per simulated trial are reported. Results are shown in [Table 10.5: 3](#).

Table 10.5: 3

Simulated operating characteristics for Arms A and B

In Scenario 1 which reflects the case of a moderate true dose-toxicity, around 29% of trials in Arm A have found an MTD with true DLT rate in the target interval. In addition to that, 288 trials [REDACTED] as MTD, which has an assumed true toxicity probability of 0.136 which is very close to the lower boundary of the target interval. In Arm B, around 82% of the simulated trials have declared a dose as MTD that has an assumed true DLT rate in the target range.

In Scenario 2 (high-toxicity scenario), around 41% of trials in Arm A and around 27% of trials in Arm B have been stopped prematurely due to too toxic doses. This is an expected situation for a high-toxicity scenario. Nevertheless, around 55% of trials in Arm A and around 61% of trials in Arm B declared a dose as MTD that has an assumed true DLT rate in the target interval.

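### The Arm B operating characteristics in Protocol Section 10.5 are inconsistent with the rule that Arm B opens only after Arm A's starting dose is cleared

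*Protocol*

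**What the plan says.** Protocol Section 3.1.1 sets the order of the arms: "Arm B will open at the starting dose level once the starting dose level in Arm A is considered safe by the SMC". Section 3.1.2 repeats it: "Once the first dose level in Arm A has been determined to be safe, Arm B may be initiated".

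Section 10.5 describes the simulation in few words. For simplicity, "a cohort size of 3 patients who are all evaluable starting at 50 µg (Arms A and B) is assumed". Later: "For each of these scenarios, 1000 trials were simulated. Each cohort consisted of 3 patients and dose escalation complied with the following rules". The rules that follow cover the escalation step and the declaration of the MTD. None makes Arm B wait for Arm A.

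The same section gives the model's response to an early DLT. After 1 DLT in 3 at Arm A's starting dose, "the model again does not allow any of the pre-specified dose levels, indicating that any DLT in the first cohort leads to recommended doses" (the dose that follows is redacted). For 1 DLT in 2, it adds that overdose control would prevent Arm B from starting at its intended dose.

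Results are given as shares of the simulated trials. The Scenario 1 result, which refers to rates inside the target range, reads: "In Arm B, around 82% of the simulated trials have declared a dose as MTD that has an assumed true DLT rate". Scenario 2: "around 41% of trials in Arm A and around 27% of trials in Arm B have been stopped prematurely due to too toxic doses", with about 61% of Arm B trials on target. For Scenario 5 the mean Arm B size is 5.0 patients.

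**The concern.** A design in which Arm B waits for Arm A loses Arm B whenever Arm A fails at its first dose. That loss depends only on Arm A's DLT rate at the starting dose and the size of the first cohort, so it can be computed exactly from the protocol. The stated Arm B results leave no room for it.

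The MTD in each arm is a primary endpoint, and Section 10.5 is the only place where the protocol quantifies how often the design finds it. A reader will take 82% and 61% as properties of the sequenced design. If Arm B was simulated even after Arm A had stopped for toxicity, they are not.

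**Working it through.** **Inputs.** True DLT rates p at Arm A's first dose come from Table 10.5: 2: 0.075 in Scenarios 1, 6 and 7 (the Scenario 1 row begins "1: Moderate A 0.075"), 0.134 in Scenario 2, 0.014 in Scenarios 3 and 4, and 0.341 in Scenario 5. Cohorts are 3 patients, with 1000 trials per scenario.

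**The plan's own figure.** The 82% cannot be reproduced exactly, because the reference dose, the dose levels and the trial 1381-0001 counts are redacted. Rebuilds with Arm B always started give 81.3% in one version and 76.5–78.9% in another.

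**Step 1: ceiling on opening (needs no redacted input).** If any first-cohort DLT in Arm A rules out all planned doses, then P(Arm B opens) ≤ (1 − p)³.

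| Scenario | (1 − p)³ | Stated for Arm B |
|---|---|---|
| 1 | 0.925³ = 79.1% | 82% on target |
| 2 | 0.866³ = 64.9% | 61% on target, 27% stopped |
| 5 | 0.659³ = 28.6% | mean 5.0 patients |
| 7 | 0.925³ = 79.1% | 74% on target |
| 3 | 0.986³ = 95.9% | 90% on target |

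- Scenario 1: 82% exceeds 79.1% even if an opened Arm B never erred. The Monte Carlo standard error is √(0.791 × 0.209/1000) = 1.3 points, so the excess of 2.9 points is about 2 standard errors. It is not decisive alone.
- Scenario 2: if unopened trials count as stopped, at least 100 − 64.9 = 35.1% must stop. The text says 27%, which is 8.1 points lower, or about 5 standard errors (√(0.649 × 0.351/1000) = 1.5 points). If they are not counted as stopped, 61 + 27 = 88% exceeds the 64.9% that could open. Both readings fail. Arm A's stated 41% stops do fit the 35.1% floor.
- Scenario 5: a mean of 5.0 over all trials needs 5.0/0.286 = 17.5 patients per opened trial. The highest Arm B mean in any scenario is 15.6.
- Scenarios 3 and 7 are not contradicted by the ceiling.

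**Step 2: approximate size.** The joint model was rebuilt from the Table 7: 1 priors, the 25% overdose limit, the 100% step cap and the stated MTD rule. Assumptions for redacted inputs:
- Reference dose 800 µg, chosen because it returns the protocol's overdose probability of 0.656 after 1 DLT in 1.
- Six doses from 50 µg to 1200 or 1600 µg.
- 0/20 or 0/56 DLTs on ezabenlimab.

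After 1 DLT in 3 in Arm A, the rebuilt overdose probability at the starting dose is about 0.30 in Arm A and 0.32–0.34 in Arm B. Both exceed 0.25, so both arms are blocked.

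| Arm B result | Stated | Always started | Opening rule applied |
|---|---|---|---|
| Sc 1 on target | 82% | 76.5–78.9% | 70.4–71.9% |
| Sc 2 on target | 61% | 57–59% | 47–50% |
| Sc 2 stopped or unopened | 27% | 27–28% | 41–42% |
| Sc 5 mean patients | 5.0 | 5.0–5.3 | 2.1 |
| Sc 7 on target | 74% | 69–71% | 65–68% |
| Sc 3 on target | 90% | 89–90% | 90–91% |

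Comparing runs made on the same assumptions, the rule costs 5–8 points in Scenario 1, 8–10 in Scenario 2 and 2–5 in Scenario 7. In Scenario 3 it costs nothing beyond simulation error.

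**Step 3: do the figures describe opened trials only?** In the runs with the rule, Scenario 1 gives 704/774 = 91% to 719/780 = 92% on target among opened trials. Scenario 2 gives 474/634 = 75% to 501/643 = 78%. The stated 82% and 61% are not these either.

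**The case against.** Four points can be made for the plan.

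**The ceiling uses the simulation's cohort size, not the trial's.** Section 3.1.2 allows a single patient at lower doses. The Scenario 1 ceiling is then 0.925 = 92.5%, or 0.925² = 85.6% with two patients, both above 82%. Section 10.5 also lets the sponsor and the SMC agree on doses below the planned levels after an early DLT. This stands: the loss in the actual trial may be smaller, and the rebuilt percentages are not estimates for it. It does not reconcile the stated figures with the 3-patient cohorts under which they were produced.

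**Arm B has opened.** Protocol Section 7 says so for version 5.0. A reader might infer that the running trial's chance of finding the Arm B MTD is overstated. The documents do not support that: given opening, the rebuilt figures are higher than the stated ones.

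**Nothing was miscounted.** A reader might infer that 82% is an arithmetical error. It may be a correct count for a simulation that starts both arms, since Section 10.5 presents the exercise as an assessment of the model. The fault is an undisclosed assumption. No sentence says that Arm B ran in every trial, so this remains an inference.

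**Little turns on it.** Dosing follows the posterior, the overdose limit and SMC review, and SAP Section 4 records that development has ended. This stands too, and limits the consequence to how the design is described.

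**Conclusion.** The inconsistency holds on the protocol's own numbers, most clearly in Scenarios 2 and 5. The stated Arm B percentages are neither the property per started trial nor the property given that Arm B opened. The likely explanation is that the simulation ignored the opening rule.

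Under the simulated 3-patient cohorts, the overstatement per started trial is roughly 5 to 10 points in Scenarios 1 and 2, smaller in Scenario 7 and nil in Scenario 3. These sizes rest on assumed values for redacted inputs and on rebuilds that vary by several points. The comparison quoted also leaves out the extra one-dose lag of Arm B in Section 3.1.1. A reader who subtracts a rebuilt figure from a stated one (for example 72% from 82%) would get a larger gap, but part of it is rebuild error.

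**What to change.** Re-run the Section 10.5 simulations with Arm B opening only as Sections 3.1.1 and 3.1.2 allow. Report Arm B results in two forms: per 1000 started trials, with the share in which Arm B never opened, and conditional on opening. Say which cohort size the opening step assumes.

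At minimum, add a statement that the present Arm B percentages do not apply the opening rule (once the sponsor has confirmed this from its simulation code) and that Arm B had already opened by version 5.0.

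The cost is a few hours of simulation and one revised table with its text. The unconditional Arm B figures will look less favourable. No patients are needed and no analysis of trial data changes.

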3. DESCRIPTION OF DESIGN AND TRIAL POPULATION

3.1 OVERALL TRIAL DESIGN AND PLAN

This study will consist of 3 arms, which will recruit patients in parallel with a clear predefined hierarchy for slot allocation ([Section 3.1.2](#)).

- Arm A: Dose escalation of BI 1387446 as single agent administered intratumourally into superficial lesions
- Arm B: Dose escalation of BI 1387446 administered intratumourally into superficial lesions, in combination with ezabenlimab (BI 754091) intravenously

Trial overview is shown in below Figure 3.1: 1.

[figure not shown]

Figure 3.1: 1 Trial overview

This study will determine the MTD as well as the safety, PK, and pharmacodynamics of BI 1387446 as monotherapy and in combination with ezabenlimab (BI 754091).

Arm A will determine the MTD for BI 1387446 intratumourally into superficial lesions as single agent. Patients with progressive disease may cross over to Arm B after completion of cycle 1, provided that Arm B is open for recruitment.

Arm B will determine the MTD for BI 1387446 intratumourally into superficial lesions in combination with ezabenlimab (BI 754091).

Arms A and B will investigate the safety, PK, and pharmacodynamics of BI 1387446 monotherapy (Arm A) or BI 1387446 in combination with ezabenlimab (BI 754091) (Arm B).

Arms A and B will start in a staggered manner (refer to [Section 3.1.1](#)).

To acquire additional data to more fully inform dose selection, additional patients may be enrolled to backfill cohorts at dose levels that have been previously cleared (refer to [Section 3.1.1](#)).

Dose escalation will be guided by Bayesian logistic regression modelling with overdose control: In Arm A and B, dose escalation will be guided by a BLRM using a hierarchical modelling approach to jointly model both arms. The data obtained from both arms will determine the MTD estimate per arm based on a BLRM employing an escalation with overdose control (EWOC) principle [[R13-4803](#)].

The BLRM estimates the MTD by updating estimates of the probability of observing a DLT in the MTD evaluation period (first treatment cycle including echocardiographic/MUGA scan measurements acquired on Day 1 of Cycle 2 and related findings) for each dose level in the trial as patient information becomes available. At any time in the trial, it will not be permitted to escalate to a dose which does not fulfil the EWOC criterion (refer to [Section 7](#)).

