In scenario 6, the data for ezabenlimab (BI 754091) largely deviates from the data for BI 1387446. While a flat dose-toxicity curve that lies in the overdose range is assumed for BI 1387446, very low toxicity is assumed for ezabenlimab (BI 754091). This results in high-toxicity for the combination arm B: Many of the simulated trials in Arm B stop prematurely because all specified dose levels are too toxic. Additionally, around 56% of trials in Arm B declare doses as MTD with true DLT rate in the overdose interval. Most of these trials choose [REDACTED] or [REDACTED] as MTD. These combinations have assumed true toxicity rates not too far away from the target rate. In Arm A, 51.6% of the simulated trials declare a dose as MTD which has an assumed true DLT rate in the underdose interval. In almost all of these cases [REDACTED] were chosen as MTD and these dose levels have an assumed true toxicity probability of 0.099 [REDACTED] and 0.136 [REDACTED]

In scenario 7 (high interaction between BI 1387446 and ezabenlimab (BI 754091)), 44.9% of the trials in Arm A declared a dose as MTD which has a true DLT rate in the underdose interval. 314 of these trials declared [REDACTED] as the MTD which has a true toxicity probability of 0.136 which is close to the lower boundary of the target interval. In Arm B around 74% of trials determined an MTD that has an assumed true toxicity rate in the target interval.

The mean patient numbers in Arm A range from approximately 5.6 patients (Scenario 5) to 17.3 patients (Scenario 3) and the maximum number of patients was 36 (Scenario 3). Similarly, for Arm B, the mean patient numbers range from 5.0 (Scenario 5) to 15.6 (Scenario 3), with a maximum number of 45 patients in a simulated trial under Scenario 3. Therefore, the patient numbers are as expected and increase when moving away from the high-toxicity scenario.

By reviewing the metrics presented in [Table 10.5: 3](#), it can be seen that the joint model is not sensitive to different scenarios of truth. Even under misspecification results are satisfactory. In general, these models are conservative due to the overdose control criteria. In all scenarios, the probabilities of recommending a dose with true $P(DLT) \geq 33\%$ as MTD are much smaller than probabilities of recommending a dose with true $P(DLT)$ between 16% and 33% as MTD.

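### Scenario 6 in the statistical appendix does not match the curve simulated for BI 1387446 monotherapy, and the closing all-scenarios statement on overtoxic MTDs is contradicted by Scenarios 5 and 6

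*Protocol*

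**What the plan says.** Protocol Section 10.5 describes Scenario 6 twice. The list of scenarios refers to a very flat curve "that lies in the overdose range (indicating a quite toxic behaviour of BI 1387446", set against ezabenlimab data that suggest very low toxicity. The results text repeats this: "While a flat dose-toxicity curve that lies in the overdose range is assumed for BI 1387446", with ezabenlimab assumed to be of very low toxicity.

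Section 3.1 defines the monotherapy arm: "Arm A: Dose escalation of BI 1387446 as single agent administered intratumourally into superficial lesions". The Arm A row is therefore the BI 1387446 single-agent curve. Table 10.5: 2 gives it as "6: Large deviation A 0.075 0.099 0.136 0.203 0.350 0.524". The Arm B row for Scenario 6 is 0.351, 0.356, 0.359, 0.361, 0.368, 0.370.

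For Scenario 6 the text reports that 51.6% of trials in Arm A declare an MTD in the underdose interval, nearly always at doses with true rates 0.099 and 0.136, and that "around 56% of trials in Arm B declare doses as MTD with true DLT rate in the overdose interval". It adds that those Arm B rates lie close to the target.

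The closing paragraphs say of the scenarios taken together: "Even under misspecification results are satisfactory". They also say that, across all scenarios, declaring an MTD with a true DLT probability of at least 33% is much less likely than declaring one between 16% and 33%.

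**The concern.** There are two separate problems. First, the description of Scenario 6 and its Arm A row cannot both be right: the text says BI 1387446 is flat and overtoxic, and the table gives its monotherapy arm a moderate, rising curve. A reader relying on the text would believe that a toxic single agent had been examined in both arms together.

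Second, the closing statement is a claim about an operating property of the design, and the appendix's own figures contradict it. The joint model is still the basis of the primary MTD analysis in SAP Section 7.4.1. Anyone judging a declared Arm B MTD should know that the simulations include a case in which more than half of trials declare an overtoxic dose, rather than read that this is uncommon throughout.

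**Working it through.** **Inputs.** True DLT rates from Table 10.5: 2; target interval [0.16, 0.33) and the no-interaction formula from Protocol Section 7; 1000 simulated trials per scenario and the result percentages from Section 10.5. The simulation itself cannot be repeated from the public text: dose levels, the BI 1387446 reference dose and the 1381-0001 data are redacted, and the body of Table 10.5: 3 is not visible.

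**Step 1: which curve Arm A was given.** Each of the six rates is classified as under / target / over:

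| Scenario | Arm A | Arm B |
|---|---|---|
| 1 | 3 / 1 / 2 | 1 / 3 / 2 |
| 2 | 1 / 3 / 2 | 1 / 2 / 3 |
| 3 | 3 / 3 / 0 | 2 / 4 / 0 |
| 4 | 3 / 1 / 2 | 2 / 1 / 3 |
| 5 | 0 / 0 / 6 | 0 / 0 / 6 |
| 6 | 3 / 1 / 2 | 0 / 0 / 6 |
| 7 | 3 / 1 / 2 | 0 / 3 / 3 |

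The Scenario 6 Arm A row equals the Scenario 1 and Scenario 7 Arm A rows at all six doses. Its spread is 0.524 − 0.075 = 0.449, and four of its six doses lie below 0.33, so it is neither flat nor overtoxic. The Arm B spread is 0.370 − 0.351 = 0.019, with every dose at or above 0.33. Only Arm B fits the description.

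**Step 2: is the Arm A row a misprint?** No. An Arm A curve lying wholly in the overdose range could not yield any underdose MTD. The text reports 51.6% underdose MTDs and cites true rates of 0.099 and 0.136, which are the second and third entries of the printed row. The moderate curve was the one run.

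**Step 3: do the two rows share one BI 1387446 curve?** Without interaction, π12 = π1 + π2 − π1π2, so π2 = (π12 − π1)/(1 − π1). With Arm A as π1 and Arm B as π12:

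- lowest dose: (0.351 − 0.075)/0.925 = 0.298
- next four: 0.285, 0.258, 0.198, 0.028
- top dose: (0.370 − 0.524)/0.476 = −0.324

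Ezabenlimab is fixed at 240 mg, so π2 should be one small number. Turned round, π1 = (π12 − π2)/(1 − π2). If π2 is assumed to be 0.005 to 0.02, Arm B implies π1 of about 0.34 to 0.37, flat and overtoxic as described. At an assumed π2 of 0.05 it implies 0.317 to 0.337, flat but straddling 0.33. The Arm B row matches the description; the Arm A row does not.

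**Step 4: the closing statement.** Where an arm has no dose in [0.16, 0.33), the probability of a target-range MTD is 0 by construction. Monte Carlo limits are p ± 1.96√(p(1 − p)/1000).

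| Scenario, arm | Overdose MTD | Monte Carlo 95% range | Target MTD |
|---|---|---|---|
| 6, B | about 56% | 52.9% to 59.1% | 0% |
| 5, A | 13.8% | 11.7% to 15.9% | 0% |
| 5, B | 12.4% | 10.4% to 14.4% | 0% |

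The overdose share exceeds the target share in all three, so the statement fails in 3 of the 14 scenario-arm combinations. In Scenario 6 Arm B, about 100% − 56% = 44% of trials are left to end without an MTD, which is the correct outcome there.

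**The case against.** The other side has real force on several points.

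- **Misspecification was tested.** A reader might infer that the robustness sentence rests on a test that was not done. The documents do not support that. A flat, overtoxic curve was run in Arm B; Section 7 gives each arm its own BI 1387446 parameters; Scenario 4, with a non-logistic curve, was simulated; and strong disagreement between arms under a borrowing model is itself a violation worth examining. What is missing is narrower: a flat, overtoxic monotherapy curve run jointly with Arm B.
- **Borrowing is not shown to be the cause.** A reader might also infer that the moderate Arm A drew Arm B towards overtoxic doses. Scenario 5 Arm B, at 12.4% against 56%, hints at this, but its curve differs. The 1381-0001 data, which enter every model fit, and Arm B rates only 0.02 to 0.04 above 0.33 are other candidates. No simulation without borrowing is reported.
- **The zero is structural.** With no target-range dose, 0% is not poor performance. This stands, and it is why the closing statement needs a restriction. It does not make the statement true.
- **Lower toxicity of the combination at the top dose** (0.370 against 0.524) is not an error in itself, since Section 7 allows negative interaction. But one negative interaction parameter would push the ezabenlimab rate needed at the lowest dose above 0.298, far from very low. Only different BI 1387446 curves in the two arms resolve this, and neither description says so.
- **Disclosure and consequence.** The 56% is reported openly, the scenario list is ambiguously worded, and the overdose criterion and MTD rules do not depend on this text. Arm B had already started by protocol version 5.0, and development has ended (SAP Section 4). Urgency is low; the statement is still wrong.

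**Conclusion.** The point holds in two parts. The Scenario 6 text contradicts the Arm A row of Table 10.5: 2, and the reported results show that the moderate row was simulated. The appendix therefore holds no run with a flat, overtoxic BI 1387446 monotherapy curve alongside Arm B. The nearest is Scenario 5, where both arms are wholly overtoxic but Arm A rises from 0.341 to 0.599.

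The all-scenarios statement is false in Scenario 6 Arm B (about 56% against 0%) and in Scenario 5 (13.8% against 0% in Arm A, 12.4% against 0% in Arm B). This conclusion takes the reported percentages as correct and otherwise needs only the printed rates and the interval limits. The remaining 11 combinations cannot be fully checked from the public text. How large the overdose share would be under the described Scenario 6 is unknown; only its target share, 0% in both arms, follows from the description.

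**What to change.** 1. Reconcile Scenario 6. Either correct both descriptions to what was run (Arm A as in Scenario 1, Arm B flat in the overdose range, with BI 1387446 behaving differently in the two arms), or re-run it with the described curve in Arm A.
2. Limit the closing statement to arms and scenarios with at least one target-range dose, after checking those against the full Table 10.5: 3.
3. Name Scenario 5 (both arms) and Scenario 6 Arm B as exceptions, with the 56%, 13.8% and 12.4% beside the structural 0%.
4. Do not ascribe the 56% to borrowing unless a simulation of Arm B without borrowing shows it.

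The cost is a few sentences in the appendix or, for the re-run, one more set of 1000 trials with existing code. The drawback is that the stated performance becomes less favourable. No decision rule or analysis changes.
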